## 17. EFFICACY OUTCOMES

Unless otherwise specified, the efficacy summary tables will include the following columns: PBO-SEP, SEP-SEP, and ALL EXT (all rollovers from SEP380-301).

All analyses of the efficacy variables will be based on the Safety Population by the actual treatment group.

### 17.1. DERIVATION & ANALYSIS OF EFFICACY VARIABLES

#### 17.1.1. CHANGES FROM DB BASELINE AND FROM OL BASELINE IN MADRS TOTAL SCORE AT EACH SCHEDULED VISIT

The MADRS (Montgomery-Asberg Depression Rating Scale) is a clinician-rated assessment of the subject's level of depression. The measure contains 10 items that measure apparent and reported sadness, inner tension, reduced sleep and appetite, difficulty concentrating, lassitude, inability to feel, and pessimistic and suicidal thoughts. Each item is scored in a range of 0 to 6 points, with higher scores indicating increased depressive symptoms. Total score will be equal to the sum of the 10 items (range between 0 and 60).

MADRS is assessed at Week 2 and monthly and at these study visits: from Visit 1E (coinciding with Visit 6 of SEP380-301) to Visit 14E.

The DB Baseline and OL Baseline MADRS total score will be derived as described in [Section 7.2](#). The change from DB Baseline and OL Baseline in MADRS total score will be derived as described in [Section 17.1.1](#).

The observed values of MADRS total score at both the DB Baseline and the OL Baseline, and at each scheduled OLE study visit (starting from Visit 1E) and LOCF, will be summarized descriptively.

Changes from DB Baseline in MADRS total score will be summarized for each scheduled OLE study visit (starting from Visit 1E) and LOCF. Changes from OL Baseline will be summarized for each scheduled post-OL Baseline extension study visit (starting from Visit 2E) and LOCF. The line plots of the mean (SD) of change from DB baseline as well as change from OL baseline will be created.

#### 17.1.2. CHANGES FROM DB BASELINE AND FROM OL BASELINE IN CGI-BP-S SCORE AT EACH SCHEDULED VISIT

The CGI-BP-S (Clinical Global Impression-Bipolar Version-Severity) is a clinician-rated assessment of the subject's current illness state on a 7-point scale, where a higher score is associated with greater illness severity. The CGI-BP-S depression score takes one of the following values: 1 (normal, not at all

ill), 2 (borderline mentally ill), 3 (mildly ill), 4 (moderately ill), 5 (markedly ill), 6 (severely ill), 7 (among the most extremely ill patients).

CGI-BP-S is assessed at week 2 and monthly and at these study visits: from Visit 1E (coinciding with Visit 6 of SEP380-301), to Visit 14E.

The DB Baseline and OL Baseline CGI-BP-S depression score will be derived as described in Section 7.2. The change from DB Baseline and OL Baseline in CGI-BP-S depression score will be derived as described in Section 17.1.2.

The observed values of CGI-BP-S depression score at both the DB Baseline and the OL Baseline, and at each scheduled OLE study visit (starting from Visit 1E) and LOCF, will be summarized descriptively.

Changes from DB Baseline in CGI-BP-S depression score will be summarized for each scheduled OLE study visit (starting from Visit 1E) and LOCF. Changes from OL Baseline will be summarized for each scheduled post-OL Baseline extension study visit (starting from Visit 2E) and LOCF. The line plots of the mean (SD) of change from DB baseline as well as change from OL baseline will be created.

#### **17.1.3. MADRS RESPONSE AT EACH SCHEDULED VISIT**

MADRS response is defined as a 50% or greater improvement (i.e., decrease) in MADRS total score from DB Baseline.

The percent change in MADRS total score from DB Baseline will be calculated by:

$$\frac{\text{MADRS total score at a visit or the LOCF endpoint} - \text{MADRS total score at DB Baseline}}{\text{MADRS total score at DB Baseline}} \times 100\%$$

For each subject, the responder indicator will be set to Y if the percent change is negative and the magnitude is equal to or greater than 50%. The indicator will be set to N if the percentage is negative but the magnitude is less than 50% or if the percentage is non-negative. The indicator will be set to missing if the percentage is missing.

MADRS response will be derived for all scheduled OLE study visits and LOCF.

The number and percentage of subjects who achieve a MADRS response will be summarized descriptively for each scheduled OLE study visit (starting from Visit 1E) and LOCF.

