15.4.2. Effectiveness Analyses

Since this is an uncontrolled open-label extension of a lead-in study of SEP-4199 CR, no inferential statistics on efficacy will be presented. All effectiveness data will be summarized by analysis group based on the safety population.

Descriptive statistics of observed values and changes from DB Baseline and OL Baseline will be summarized by study visit and analysis group for effectiveness parameters (continuous). At a visit in the extension study, responders relative to DB Baseline are defined as those who show a 50% or more reduction (ie, improvement) from DB Baseline in MADRS total score. At a post-OL Baseline visit, responders relative to OL Baseline are defined as those who show a 50% or more reduction (ie, improvement) from OL Baseline. Remitters at any visit are defined as a subjects with a MADRS total score of \leq 12. Frequencies and percentages of MADRS responders relative to both DB Baseline and OL Baseline, and frequencies and percentages of remitters will be summarized over time by analysis group.

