### **3.2.3. EFFECTIVENESS ENDPOINTS**

- Changes in MADRS total score
- Changes in CGI-BP-S depression score
- The proportion of subjects with treatment response, defined as  $\geq 50\%$  reduction from Baseline in MADRS total score
- The proportion of subjects meeting criteria for remission, defined as MADRS total score  $\leq 12$
- Changes in HAM-A total score

- Changes in QIDS-SR16 total score
- Changes in SDS total and subscale scores (work/school, family, and social function)
- The proportion of subjects meeting criteria for functional remission, defined as having a score  $\leq 2$  on each of the SDS subscale scores (work/school, family, and social function)
- Changes in the EQ-5D-5L Visual Analog Scale (VAS) and Index scores
- Changes in the SHAPS total score

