## 4.7. CHANGES TO ANALYSIS FROM PROTOCOL

Because of the small sample size due to study early termination, the following main changes will be made for this study:

- Only 2 treatment groups will be formed based on a subject's previous participation in the lead-in study of SEP-4199 CR (SEP-SEP: previously randomized to any SEP-4199 CR dose group and PBO-SEP: previously randomized to placebo).
- No subgroup summaries will be performed.
- No summaries using Follow-up population will be performed.
- Except for PWC, follow-up period summaries will not be performed, PWC will be summarized by Safety population.
- AE will not be summarized by high-level term (HLT).
- No Kaplan-Meier curves will be plotted for time to discontinuation and time to the earliest onsets of the selected AESI. The Kaplan-Meier estimation will also not be performed.
- To be consistent with AIMS and BARS, MSAS will be summarized by total score.

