## 17.2. MISSING DATA

Any individual missing item in any scale will not be imputed.

For derived scores that depend on more than one individual item (e.g., MADRS total score, EQ-5D-5L index score), if one or more items are missing at a visit, the derived score will be set to missing. The corresponding change from DB Baseline or OL Baseline value at a given time point will be set to missing if the DB Baseline or OL Baseline derived score is missing or if the derived score at that time point is missing.

For MADRS response compared to DB Baseline, any subject with a missing MADRS total score at DB Baseline or at any scheduled OLE study visit (starting from Visit 1E) or LOCF will have their MADRS response set to missing for that time point.

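### SAP 17.1.3 derives MADRS response from DB Baseline only; the OL Baseline responder rate planned in Protocol 15.4.2 is missing, and SAP 4.7 does not list its removal

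*SAP*

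**What the plan says.** Protocol 15.4.2, repeated in the synopsis under Statistical Methods, defines MADRS response against two references. One is DB Baseline. For the other, at visits after OL Baseline, "responders relative to OL Baseline are defined as those who show a 50% or more reduction (ie, improvement) from OL Baseline". The commitment to report covers both: "Frequencies and percentages of MADRS responders relative to both DB Baseline and OL Baseline, and frequencies and percentages of remitters will be summarized" over time and by analysis group.

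SAP 17.1.3 defines one rate: "MADRS response is defined as a 50% or greater improvement (i.e., decrease) in MADRS total score from DB Baseline". Its percent-change formula uses the DB Baseline score throughout, and the counts "will be summarized descriptively for each scheduled OLE study visit (starting from Visit 1E) and LOCF". The missing-data rule in SAP 17.2 opens "For MADRS response compared to DB Baseline, any subject with a missing MADRS total score at DB Baseline" and has no counterpart for OL Baseline. The endpoint list in SAP 3.2.3 does not settle the matter. It reads "The proportion of subjects with treatment response, defined as" a reduction of at least 50% from Baseline, without saying which baseline.

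SAP 4.7 gives seven main changes from the protocol and attributes them to the small sample after early termination. The first is "Only 2 treatment groups will be formed based on a subject's previous participation in the lead-in study". None concerns MADRS response or the OL Baseline reference.

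**The concern.** There are two linked problems.

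The first is traceability. The protocol specifies a table, the SAP does not produce it, and the section meant to record departures does not mention it. The reason given in SAP 4.7 does not explain the gap either, because the DB Baseline rate is kept in the same subjects.

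The second is interpretation in PBO-SEP. These subjects took placebo in the lead-in study (SAP 6.1). DB Baseline is the last value before the first lead-in dose, and OL Baseline is the last value before the first open-label dose (SAP 7.2). A rate measured from DB Baseline therefore spans six weeks of placebo followed by open-label SEP-4199 CR. In SEP-SEP the same rate spans treatment assigned to SEP-4199 CR throughout, and ALL EXT pools the two groups. The missing rate was the only planned responder rate measured from the start of open-label drug.

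**Working it through.** **Text comparison**

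| Item | Protocol 15.4.2 | SAP |
|---|---|---|
| Response from DB Baseline | defined, to be tabulated | defined and tabulated (17.1.3) |
| Response from OL Baseline | defined, to be tabulated | absent |
| Missing-data rule, DB Baseline | left to the SAP (15.4.6) | given (17.2) |
| Missing-data rule, OL Baseline | left to the SAP (15.4.6) | absent |
| Continuous MADRS change from both baselines | planned | kept, with line plots (17.1.1) |
| Removal listed as a change | not applicable | not in 4.7 |

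The other continuous effectiveness measures in SAP 17.1 (CGI-BP-S, HAM-A, QIDS-SR16, SDS, EQ-5D-5L, SHAPS) also keep both references. Response is the only baseline-relative effectiveness outcome derived there that loses one. That pattern suggests an oversight, although the documents do not say so.

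**Effect of the reference on one subject**

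The SAP formula is percent change = (visit score − baseline) / baseline × 100, with response if this is −50% or lower. The scores below are constructed for a PBO-SEP subject.

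| DB Baseline | OL Baseline | Later visit | From DB Baseline | From OL Baseline |
|---|---|---|---|---|
| 32 | 15 | 15 | (15−32)/32 = −53.1%, responder | (15−15)/15 = 0%, not |
| 40 | 24 | 20 | (20−40)/40 = −50.0%, responder | (20−24)/24 = −16.7%, not |
| 30 | 36 | 18 | (18−30)/30 = −40.0%, not | (18−36)/36 = −50.0%, responder |

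In the first row the whole fall precedes any open-label dose, and the subject is already a responder at Visit 1E. In the second row (40−24)/(40−20) = 80% of the fall precedes it. The third row shows that the disagreement can run the other way.

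**Group-level illustration (assumptions, not document figures)**

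The documents give no MADRS means or SDs and no lead-in response rates. A simulation assumed DB Baseline mean 30 and SD 5 with a floor of 20, and a placebo-phase change with mean −6, −10 or −14 and SD 9, independent of baseline.

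- With no open-label change, DB Baseline responders are 17%, 30% or 47% at every visit, including Visit 1E. OL Baseline responders are 0%.
- With a mean open-label change of −4 or −8 (SD 5), the DB Baseline rate runs from 33% to 75% and the OL Baseline rate from 13% to 45%. Of the DB Baseline responders, 40% to 61% are not OL Baseline responders, and 36% to 72% already met the definition at Visit 1E.

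**The case against.** The case for leaving the SAP as it stands has real weight.

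- **The table shows the carry-in.** SAP 17.1.3 tabulates response from Visit 1E, which is the day before the first open-label dose (note to SAP Figure 1), and PBO-SEP has its own column. A reader might infer that no responder output separates the two periods. That is too strong, because the Visit 1E row is the PBO-SEP response rate at the end of placebo.
- **Open-label change is reported elsewhere.** SAP 17.1.1 keeps continuous MADRS change from OL Baseline from Visit 2E and at LOCF, by group. Remission (17.1.4) needs no baseline.
- **The SAP does not mislabel the rate.** A reader might infer that placebo improvement is being presented as response to open-label SEP-4199 CR. SAP 17.1.3 says only that response is measured from DB Baseline. Protocol 15.4 makes that the general reference, and Protocol 15.4.2 plans this rate.
- **The OL Baseline rate is not a measure of drug effect.** The study is uncontrolled, and both documents rule out inference. The rate also behaves awkwardly at low scores: from an OL Baseline of 15 a subject must reach 7 (8 gives only −46.7%), while a move from 4 to 2 counts as response.
- **SAP 4.7 claims only to list main changes**, so absence from it does not show concealment.

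All of this stands and limits the point, but it does not supply the missing table. The general allowance in Protocol 15.4 for OL Baseline changes where relevant does not help, since 15.4.2 names the OL Baseline responder rate explicitly. SAP 4.7 also records changes as small as dropping high-level-term summaries. Subtracting the Visit 1E rate from a later rate does not recover new responders. Missing scores give missing response, so the contributing subjects differ by visit, and losses of response offset gains.

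**Conclusion.** The omission is established from the text: a responder rate specified in the protocol is absent from the SAP and its removal is unrecorded. For PBO-SEP, and for ALL EXT through pooling, the retained rate mixes placebo-period and open-label change. Group-level carry-in remains visible, but no planned summary identifies subjects who newly reached a 50% reduction after starting open-label SEP-4199 CR.

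The defect is the missing second rate, not the DB Baseline rate. Its numerical size cannot be derived from the documents, and the 17% to 47% carry-in range rests wholly on the assumed means and SDs. The importance is modest. Effectiveness is secondary to the safety objective, the analysis is descriptive, and SAP 4.4 reports 64 enrolled subjects, of whom PBO-SEP is a subset of unstated size.

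**What to change.** In SAP 17.1.3, add response relative to OL Baseline beside the DB Baseline rate: a decrease of at least 50% from the OL Baseline MADRS total score, at each scheduled visit from Visit 2E and at LOCF, by treatment group. In SAP 17.2, add the matching rule that response is missing if the OL Baseline score or the visit score is missing. State also how an OL Baseline score of 0 is handled, since percent change is then undefined. Naming both references in SAP 3.2.3 would remove the ambiguity there.

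If the sponsor prefers not to produce the table, SAP 4.7 should list the removal and give the reason. Restoring it costs one derived flag and one table block, with no new data collection.

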#### **17.1.4. MADRS REMISSION AT EACH SCHEDULED VISIT**

MADRS remission is defined as MADRS total score  $\leq 12$ .

For each subject, the remitter indicator will be set to Y if the MADRS total score is less than or equal to 12. The indicator will be set to N if the MADRS total score is more than 12. The indicator will be set to missing if the MADRS total score is missing.

MADRS remission will be derived for all scheduled OLE study visits and LOCF.

The number and percentage of subjects who achieve a MADRS remission will be summarized descriptively for each scheduled OLE study visit (starting from Visit 1E) and LOCF.

#### **17.1.5. CHANGES FROM DB BASELINE AND FROM OL BASELINE IN HAM-A TOTAL SCORE AT EACH SCHEDULED VISIT**

The Hamilton Anxiety Rating Scale (HAM-A) is a clinician-administered scale that was developed to quantify the severity of anxiety symptomatology. It consists of 14 items, each defined by a series of symptoms. Each item is rated on a 5-point (0-4) scale, with higher scores indicating greater severity.

HAM-A total score will be equal to the sum of the 14 items and ranges between 0 and 56.

HAM-A is assessed at these study visits: Visit 1E (coinciding with Visit 9 of SEP380-301), Visit 4E, Visit 6E, Visit 8E, Visit 10E, Visit 12E, and Visit 14E.

The DB Baseline and OL Baseline HAM-A total score will be derived as described in [Section 7.2](#). The change from DB Baseline and OL Baseline in HAM-A total score will be derived as described in [Section 17.1.5](#).

The observed values of HAM-A total score at both the DB Baseline and the OL Baseline, and at each scheduled OLE study visit (starting from Visit 1E) and LOCF, will be summarized descriptively.

Changes from DB Baseline in HAM-A total score will be summarized for each scheduled OLE study visit (starting from Visit 1E) and LOCF. Changes from OL Baseline will be summarized for each scheduled post-OL Baseline extension study visit (starting from Visit 4E) and LOCF.

#### **17.1.6. CHANGES FROM DB BASELINE AND FROM OL BASELINE IN QIDS-SR16 TOTAL SCORE AT EACH SCHEDULED VISIT**

The Quick Inventory of Depressive Symptomatology – Self Report (QIDS-SR16) is a 16-item subject-reported depression symptom severity questionnaire. Each item is rated 0 to 3. The scoring of the QIDS-SR16 converts responses to 16 separate items into the 9 DSM-IV symptom criterion domains. The 9 domains are: sad mood (Item 5), concentration (Item 10), self-criticism (Item 11), suicidal ideation (Item 12), interest (Item 13), energy/fatigue (Item 14), sleep disturbance (early/middle/late insomnia or hypersomnia) (Items 1 to 4), decrease/increase in appetite/weight (Items 6 to 9), and psychomotor agitation/retardation (Items 15 and 16). For symptom domains that consist of more than one item, the highest score among the items relevant to the given domain is taken. The total score will be equal to the sum of the 9 domains and ranges from 0-27 with higher scores indicating greater severity.

QIDS-SR16 is assessed at these study visits: Visit 1E (coinciding with Visit 9 of SEP380-301), Visit 4E, Visit 6E, Visit 8E, Visit 10E, Visit 12E, and Visit 14E.

The DB Baseline and OL Baseline QIDS-SR16 total score will be derived as described in Section 7.2. The change from DB Baseline and OL Baseline in QIDS-SR16 total score will be derived as described in Section 17.1.6.

The observed values of QIDS-SR total score at both the DB Baseline and the OL Baseline, and at each scheduled OLE study visit (starting from Visit 1E) and LOCF, will be summarized descriptively.

Changes from DB Baseline in QIDS-SR total score will be summarized for each scheduled OLE study visit (starting from Visit 1E) and LOCF. Changes from OL Baseline will be summarized for each scheduled post-OL Baseline extension study visit (starting from Visit 4E) and LOCF.

#### **17.1.7. CHANGES FROM DB BASELINE AND FROM OL BASELINE IN SDS TOTAL SCORE AND SUBSCALE SCORES AT EACH SCHEDULED VISIT**

The Sheehan Disability Scale (SDS) is a subject-reported assessment of function. The SDS is a composite of 3 items designed to measure the extent to which 3 major sectors in a patient's life are impaired by depressive symptoms. This anchored visual analogue scale uses spatiovisual, numeric, and verbal descriptive anchors simultaneously to assess disability across 3 domains: work, social life or leisure activities, and home life or family responsibilities. The subject will rate his or her degree of impairment in each of these domains using an 11-point scale ranging from 0-10, with higher scores indicating more impairment. There are verbal descriptors for the points on the scale as well as numerical scores that provide more precise levels of the verbal descriptors. Scores for the 3 items are summed into a single dimensional measure of global functional impairment that ranges from 0 (unimpaired) to 30 (highly impaired).

SDS is assessed at these study visits: Visit 1E (coinciding with Visit 9 of SEP380-301), Visit 4E, Visit 6E, Visit 8E, Visit 10E, Visit 12E, and Visit 14E.

The DB Baseline and OL Baseline SDS total score will be derived as described in [Section 7.2](#). The change from DB Baseline and OL Baseline in SDS total score will be derived as described in [Section 17.1.7](#).

The observed values of SDS total score at both the DB Baseline and the OL Baseline, and at each scheduled OLE study visit (starting from Visit 1E) and LOCF, will be summarized descriptively.

Changes from DB Baseline in SDS total score will be summarized for each scheduled OLE study visit (starting from Visit 1E) and LOCF. Changes from OL Baseline will be summarized for each scheduled post-OL Baseline extension study visit (starting from Visit 4E) and LOCF.

#### **17.1.8. CHANGES FROM DB BASELINE AND FROM OL BASELINE IN EQ-5D-5L VAS AND INDEX SCORES AT EACH SCHEDULED VISIT**

The EuroQol-5 Dimensions – 5 Levels (EQ-5D-5L) is a standardized instrument developed by the EuroQol Group as a measure of health-related quality of life that can be used in a wide range of health conditions and treatments. The EQ-5D-5L consists of two parts: a) the EQ-5D-5L descriptive system, and b) the EQ VAS.

The EQ-5D-5L descriptive system comprises five dimensions: mobility, self-care, usual activities, pain/discomfort, and anxiety/depression. Each dimension has 5 levels: level 1 (no problems), level 2 (slight problems), level 3 (moderate problems), level 4 (severe problems), and level 5 (extreme problems/unable to do). The patient is asked to indicate his/her health state by ticking the box next to the most appropriate statement in each of the five dimensions. This decision results in a 1-digit number that expresses the level selected for that dimension (i.e., the index score).

The index scores for the five dimensions can be combined into a 5-digit code that describes the patient's health state. An index value (a weighted scoring of the 5 dimension scores with a possible range from less than 0 [where 0 is the value of a health state equivalent to dead; negative values representing values as worse than dead] to 1 [the value of full health]) will be assigned to each observed health state using the US standard value set as defined in [APPENDIX 3](#).

The EQ VAS records the patient's self-rated health on a vertical visual analogue scale from 0 to 100, where the endpoints are labelled 'The best health you can imagine' and 'The worst health you can imagine'. The VAS can be used as a quantitative measure of health outcome that reflect the patient's own judgment.

EQ-5D-5L is assessed at these study visits: Visit 1E (coinciding with Visit 9 of SEP380-301), Visit 4E, Visit 6E, Visit 8E, Visit 10E, Visit 12E, and Visit 14E.

The DB Baseline and OL Baseline EQ-5D-5L VAS and Index scores will be derived as described in Section 7.2. The change from DB Baseline and OL Baseline in EQ-5D-5L VAS and Index scores will be derived as described in [Section 17.1.8](#).

The observed values of EQ-5D-5L VAS and Index scores at both the DB Baseline and the OL Baseline, and at each scheduled OLE study visit (starting from Visit 1E) and LOCF, will be summarized descriptively.

Changes from DB Baseline in EQ-5D-5L VAS and Index scores will be summarized for each scheduled OLE study visit (starting from Visit 1E) and LOCF. Changes from OL Baseline will be summarized for each scheduled post-OL Baseline extension study visit (starting from Visit 4E) and LOCF.

